### **Expected outcomes:**

Specific Aim 1: FMD and RHI at 24 hours post-transfusion with saRBCs will be lower than following transfusion of fresh RBCs in the same patient.

Specific Aim 2: Exercise tolerance and VO2Max will increase following fresh RBC transfusions; in contrast, transfusion of saRBC will either lead to a lesser increase in these markers or will produce an actual decrease in these parameters.

Secondary Endpoints: Markers of oxidative stress (glutathione and cysteine redox ratios) and inflammatory markers will show a greater increase following saRBC transfusion than after fresh transfusions.

### **Potential Limitations and Alternative Techniques:**

Since we have previously observed significant differences in FMD following transfusion of saRBCs, but not fresh RBCs, in hospitalized subjects, we do not anticipate difficulty measuring vascular reactivity in response to transfusion in this ambulatory chronically-transfused patient population. In fact, the proposed design using outpatients allows for improved adherence to optimal FMD and PAT technique including control of study timing relative to transfusions, medications, diet and circadian rhythms. Furthermore, a cross-over design allows for control of inter-individual variation which was a significant limitation of our prior mechanistic studies. It is possible that some of these patients do not have the level of preexisting endothelial dysfunction we observed in the hospitalized population. If this is the case, and it turns out to limit our ability to measure the physiologic effects of saRBC transfusions, we can narrow the study population to transfusion dependent-individuals with baseline cardiovascular disease.

Given that this is a chronically ill population, we may have difficulty recruiting participants who are able to complete the CPX procedure. However, as demonstrated by our preliminary data in patients with peripheral arterial disease, we have previously had success measuring exercise outcomes in other populations with functional physical limitations. We are also prepared to employ other exercise protocols, if necessary, including the modified Balke or Gardner protocols for use with treadmill testing, or by utilizing a seated cycle ergometer as opposed to treadmill.

### **Statistical considerations:**

Sample size justification for Aim 1: Subject numbers are based on the primary objective (Aim 1) of measuring change in FMD (%) with transfusion. For sample size calculations, we use the paired t-test statistic and assume a two-sided test with  $\alpha=0.05$  and power = 0.8. Based on the FMD changes we observed in transfused hospitalized patients (see preliminary data) of 2.4% with saRBC transfusion and a standard deviation of FMD in our lab of 3.11%, with a sample size of 24 we have power to observe a 0.85% change in FMD with blood transfusion. This is a clinically meaningful change.

Sample size justification for Aim 2: Subject numbers are based on the primary objective of measuring change in VO2Max with transfusion of fresh vs saRBCs (Aim 2). A sample size of 24 achieves 86% power to detect a VO2Max difference of 130 ml/min between fresh and saRBC transfusions. These calculations are based on a mean of 1100 and the alternative hypothesis mean of 1230 with an estimated standard deviation of 190.0 and with a significance level (alpha) of 0.05 using a two-sided Wilcoxon test assuming that the actual distribution is normal. This calculation is based on published VO2Max responses to exercise in an anemic population.

Statistical analysis will be performed in consultation with faculty statisticians within the Emory Clinical Cardiovascular Research Institute. Descriptive statistics will be performed initially by calculating means, standard deviation, range, descriptive plots, and box-plot histograms for each variable. This will assist in determining distributional properties of the outcome variable and the choice of appropriate subsequent analytical approaches (parametric vs non-parametric). For most analyses, we will use a generalized linear mixed model to analyze these data provided that outcomes are normally distributed. Otherwise we will use transformation methods. Given that there are multiple hypotheses with multiple outcomes it is necessary to adjust for multiple comparisons. With the proposed sample size, we will not adjust for multiple comparisons with different outcomes but will adjust for comparisons within each outcome. The sample size may be too small for certain outcomes given the heterogeneity of subjects: therefore we will interpret results carefully, particularly with secondary outcomes. In such cases we will report the confidence intervals.

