**Aim 1:** *To assess the effects of fresh vs. saRBC transfusions on NO-dependent endothelial function in chronically anemic adults using: 1) flow mediated dilation (FMD) and 2) reactive hyperemic index (RHI) measured by pulsatile arterial tonometry (PAT). The primary endpoint of this Aim is the change in FMD with fresh vs. saRBC transfusion. The secondary endpoint is change in RHI.*

**Aim 2:** *To assess the effects of fresh vs. saRBC transfusions on functional exercise capacity and oxygen carrying capacity by cardiopulmonary exercise testing. The primary endpoint is the change in peak oxygen consumption (VO2Max) after transfusion.*

**Secondary endpoints** for the above Aims are changes in metabolic markers before and after transfusion/exercise: inflammation (IL-2, IL-6, hsCRP), oxidative stress (glutathione/glutathione disulfide and cysteine/cystine redox potentials), and nitric oxide metabolites (nitrite, nitrate, and nitrosylated hemoglobin and thiols).

These studies are a continuation of research I performed during my postdoctoral fellowship and represent an interdisciplinary approach with mentoring expertise in transfusion medicine and cardiovascular function. These novel studies will be crucial for my continued research training, and will provide data to support future independent NIH funding to further dissect the mechanisms of the adverse effects of saRBC transfusions and to develop approaches to abrogate those effects.

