### **Study Measurements:**

Endothelial function assessment -- Brachial artery flow-mediated vasodilation (FMD): All studies will be performed in a temperature-controlled vascular laboratory after an overnight fast. The brachial artery of the non-dominant arm will be imaged using a high-resolution 13 MHz ultrasound transducer (Acuson) as previously described in detail and as used for the studies shown in Fig 3 of the preliminary results section. Briefly, a blood pressure cuff on the forearm will be inflated to supra-systolic pressures to produce 5 minutes of ischemia. On cuff deflation, reactive hyperemia produces an acute increase in shear stress with an accompanying release of NO. Imaging of the brachial artery is performed continuously for the next 120 seconds, providing the data necessary to calculate flow-mediated dilation. After a 10 minute recovery interval, sublingual nitroglycerin will be given (0.4 mg) and the brachial artery will be re-imaged after 3 minutes. Image analysis will be performed by an experienced FMD investigator who is blinded to the treatment arm. Arterial diameter will be measured using a validated proprietary software program (Medical Instruments Inc.). Brachial artery FMD will be calculated as [(postischemia diameter - baseline diameter) / baseline diameter] X 100.

Reproducibility: FMD is well-accepted technique. In our laboratory, the mean difference in FMD (%) between 2 consecutive assessments performed in 11 subjects an average of 8 days apart was 1.26% ( $\pm 0.76\%$ ,  $r=0.75$ ). The mean difference in the FMD (%) between 2 readings of the same 11 measurements was 0.82% ( $\pm 0.48\%$ ,  $r=0.97$ ). (unpublished data)

Endothelial function assessment – Reactive Hyperemia Index (RHI) as measured using Pulsatile Arterial Tonometry (PAT, Itamar Medical Ltd.): This assay uses a device that measures reactive hyperemia of the finger. The magnitude of hyperemia correlates with coronary microvascular endothelial function, peripheral vascular endothelial function measured as brachial reactivity, and can be inhibited by LNG monomethyl arginine, indicating that it is NO-dependent. We are employing this technique currently in our catheterization lab population and have found it to be easy to use and reproducible.

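### The 0.85% detectable FMD change stated for Aim 1 does not follow from the inputs given with it

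*Combined protocol and SAP*

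**What the plan says.** The sample size paragraph for Aim 1, under Statistical considerations, sets out the method: "For sample size calculations, we use the paired t-test statistic and assume a two-sided test with" alpha 0.05 and power 0.8. It offers two numerical inputs. One is a change seen earlier in hospitalized patients, "of 2.4% with saRBC transfusion". The other is "a standard deviation of FMD in our lab of 3.11"%. It then concludes that "with a sample size of 24 we have power to observe a 0.85% change in FMD with blood transfusion", and calls that change clinically meaningful. It gives no SD for a paired difference and no within-subject correlation.

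Two other places bear on the calculation:

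- Specific Aims, Aim 1, defines the endpoint: "The primary endpoint of this Aim is the change in FMD with fresh vs. saRBC transfusion". FMD is measured before and after each of the two transfusions (Study Design).
- Study Measurements reports reproducibility from the same laboratory. The mean difference between "2 consecutive assessments performed in 11 subjects an average of 8 days apart was 1.26"% (± 0.76%), with r = 0.75. The sample size paragraph does not refer to these data.

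**The concern.** A paired t-test depends on the SD of the within-subject contrast. The only SD supplied is 3.11%, described as the SD of FMD in the laboratory. A detectable change of 0.85% is about a quarter of that (0.85/3.11 = 0.27), which is small for 24 pairs at 80% power.

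This is the only power statement for the Aim 1 primary endpoint. A reader will take it that the trial has 80% power for 0.85%, and may read a null result as evidence against an effect of that size. If the true sensitivity is lower, that inference fails.

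**Working it through.** **Inputs.** From Statistical considerations: paired t-test, two-sided alpha 0.05, power 0.80, n = 24, SD 3.11%, stated detectable change 0.85%. From Study Measurements: retest difference 1.26 ± 0.76% in 11 subjects, r = 0.75. All FMD figures are in FMD percentage points.

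**Attempt to reproduce 0.85%.** Power comes from the noncentral t with 23 degrees of freedom. Solving for 80% power gives

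detectable difference = 0.5972 × SD of the contrast.

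The normal approximation gives (1.960 + 0.842)/√24 = 0.572 × SD.

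With SD 3.11%: 0.5972 × 3.11 = 1.86%, more than twice the stated figure. Power at 0.85% is 25%, and 80% power at 0.85% would need n = 108. Relaxing the settings does not recover the figure: a one-sided test gives 1.63%, and 50% power gives 1.30%.

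**What 0.85% requires.**

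- Contrast SD: 0.85/0.5972 = 1.423%.
- If 3.11% is a single-reading SD and the contrast is one pair of readings, SD² = 2 × 3.11² × (1 − r). Then r = 1 − 1.423²/(2 × 3.11²) = 0.895.
- If the contrast is a difference of two changes (four readings, equal correlations assumed), SD² = 4 × 3.11² × (1 − r). Then r = 1 − 1.423²/(4 × 3.11²) = 0.948.

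**Readings the documents allow.** None is shown to be the intended one.

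- A: 3.11% is the SD of the paired contrast.
- B: 3.11% is a single-reading SD, r = 0.75, one pair: 3.11 × √(2 × 0.25) = 2.20%.
- C: as B, for a difference of two changes, with r = 0.75 between all readings (assumption): 3.11 × √(4 × 0.25) = 3.11%.
- D: retest data read as the mean and SD of absolute differences (assumption), one pair: √(1.26² + 0.76²) = 1.47%.
- E: as D, for a difference of two changes with independent errors: 1.471 × √2 = 2.08%.

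| Reading | SD of contrast | Detectable, n = 24 | Power at 0.85% | n for 80% power at 0.85% |
|---|---|---|---|---|
| A | 3.11% | 1.86% | 25% | 108 |
| B | 2.20% | 1.31% | 44% | 55 |
| C | 3.11% | 1.86% | 25% | 108 |
| D | 1.47% | 0.88% | 77% | 26 |
| E | 2.08% | 1.24% | 48% | 49 |

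Under D the normal approximation gives 0.572 × 1.471 = 0.84%.

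**Signed differences.** If 1.26 ± 0.76 describes signed differences, it is a systematic drift between visits: t = 1.26/(0.76/√11) = 5.5. The contrast SD would be 0.76% for one pair, or 0.76 × √2 = 1.075% for two changes. The detectable differences would be 0.45% and 0.64%. That is better than claimed, but still not 0.85%.

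**The case against.** The best defence is that the figure is under-documented and not shown to be false. The plan supplies an SD of FMD, which on its face is not the SD of a paired contrast. The decisive input is missing, and a missing input does not disprove the result.

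Reading D strengthens this. A retest SD of 1.47% combined with a single-reading SD of 3.11% implies r = 1 − 1.471²/(2 × 3.11²) = 0.888, against the 0.895 required (0.886 by the normal approximation). The reported r = 0.75 cannot rule that out: with 11 subjects its 95% Fisher-z interval is about 0.27 to 0.93, and a correlation from a small sample need not hold in a more varied group. The paragraph also speaks of change with transfusion, and Expected outcomes compares 24-hour FMD between products. Both suggest one pair of readings, which would set C and E aside. Finally, at the cited 2.4% change, 24 subjects give at least 95% power on every reading from A to E.

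Much of this stands. It is not shown that 0.85% is unattainable, B and C rest on an imprecise correlation, and the choice of contrast is open. But D needs an unstated interpretation of ± 0.76%, is not cited in the paragraph, and gives 1.24% if the endpoint is a difference of two changes. The 2.4% is the change after saRBC in inpatients. It is not the fresh-minus-saRBC difference, and power at 2.4% does not support a claim about 0.85%.

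**Conclusion.** The concern holds. The stated 80% power for 0.85% cannot be obtained from the stated test, sample size and SD. It needs a contrast SD of about 1.42%, or a within-subject correlation of about 0.895 (one pair) or 0.948 (difference of two changes, equal correlations) if 3.11% is a single-reading SD. The paragraph gives none of these. On readings A to E the detectable difference is 0.88% to 1.86%, so the stated figure is optimistic by a little or by more than a factor of two. Only the signed-difference reading is more favourable, and it implies a drift between visits.

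The calculations assume 24 subjects evaluable in both periods. The conclusion concerns the stated sensitivity only. It does not settle whether 24 subjects are adequate.

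**What to change.** Replace the 0.85% claim. State which FMD contrast will be tested, the SD of that contrast (or the single-reading SD with the within-subject correlation), and the source. Reconcile the choice with the retest data in Study Measurements, saying whether those differences are signed or absolute. Suggested text:

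> With 24 evaluable subjects, a paired t-test (two-sided alpha 0.05) has 80% power for a fresh-minus-saRBC difference of X FMD percentage points in [contrast tested], assuming an SD of that difference of Y% from [source].

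Here X = 0.597 × Y. For illustration only, Y = 3.11 gives 1.86, 2.20 gives 1.31, 2.08 gives 1.24, and 1.47 gives 0.88. The factor holds for 24 subjects with both periods evaluable. Recompute it if fewer are expected, for instance because patients are excluded when units of the required age are unavailable (Procedures). Keep the description as clinically meaningful only if the cited source supports the restated figure.

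The cost is one rewritten paragraph and possibly a less favourable stated sensitivity. No change to the sample size or the analysis is asked for here.

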## **Specific Aims:**

**Aim 1:** To assess the effects of fresh vs. saRBC transfusions on NO-dependent endothelial function in chronically anemic adults using: 1) flow mediated dilation (FMD) and 2) reactive hyperemic index (RHI) measured by pulsatile arterial tomography (PAT). The primary endpoint of this Aim is the change in FMD with fresh vs. saRBC transfusion; The secondary endpoint is change in RHI.

**Aim 2:** To assess the effects of fresh vs. saRBC transfusions on functional exercise capacity and oxygen carrying capacity by cardiopulmonary exercise testing. The primary endpoint is the change in peak oxygen consumption (VO2Max) after transfusion.

**Secondary endpoints** for the above Aims are changes in metabolic markers before and after transfusion/exercise: inflammation (IL-2, IL-6, hsCRP), oxidative stress (glutathione/glutathione disulfide and cysteine/cystine redox potentials), and nitric oxide metabolites (nitrite, nitrate, SNO-Hb and SNO-thiols).

**Hypotheses:** In patients with chronic transfusion-dependent anemia, transfusion of saRBCs will impair vascular reactivity compared to transfusion of fresh RBCs (Aim 1). Impairment of NO-mediated vasodilation will be associated with decreased exercise tolerance and peak oxygen consumption (VO2Max) following saRBC transfusion as compared to fresh RBCs (Aim 2), and will be associated with increased systemic oxidative stress and inflammation, and decreased circulating NO metabolites (Secondary endpoints).

[figure not shown]

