**Study Design:** Studies will be performed in a temperature-controlled vascular laboratory in the outpatient unit of the Clinical Research Network, ACTSI, at Emory University Hospital after an overnight fast. After providing informed consent, subjects will be randomized to receive their next clinically-indicated outpatient transfusion with fresh (<10 days old) blood or storage-aged (>21 day old) blood. Following their first transfusion, subjects will be crossed-over to receive the opposite aged product. Subjects and individuals conducting and interpreting experimental tests will be blinded to the age of RBC units. To maintain safety, clinical staff will not be blinded. All subjects will receive clinically indicated transfusions with cross-matched, leukoreduced AS1 units of packed RBCs from available blood bank inventory. The effects of RBC transfusion on blood flow and peripheral O2 delivery will be directly tested in the 24 volunteers using non-invasive assessments of endothelial function including: brachial artery flow-mediated dilation (FMD) and pulsatile arterial tonometry (PAT). Symptoms of fatigue and anemia will be objectively assessed at every visit using the self-administered FACT-An questionnaire (Functional Assessment of Cancer Therapy – Anemia). Vascular function will be assessed prior to transfusion as well as 1 hour and 24 hours after blood transfusion. Concurrently, subjects will undergo cardiopulmonary following each transfusion. Blood samples will be obtained at baseline, prior to and following each transfusion and from each unit transfused to perform metabolic marker testing.

**Study Schedule (Figure 4, below):** Each subject will be studied over a total of 4 visits, as shown in the Figure and described below.

**Screening:** Subjects will be screened with history and physical for inclusion and exclusion criteria and provide written consent. Subjects to meet inclusion and exclusion criteria, and give consent, will be randomized into either Group A or Group B.

**Visit #1 (Transfusion #1):** Subjects will return fasting to receive a scheduled, clinically-indicated RBC transfusion. Depending on their randomization to Group A or B, they will receive either fresh or saRBCs; an infusion pump will be used to administer the blood over a 1 hour period. FMD and PAT and will be performed and blood samples will be obtained for measurement of oxidative stress and other metabolic markers prior to and 1 hour following RBC transfusion.

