## **Procedures:**

Blood Transfusion: Participants will receive either 1 or 2 packed RBC units as ordered by their attending physician. Units will be infused intravenously via programmable electronic infusion pump (Baxter, Inc) over 1 hour per unit. The subjects will receive only cross-matched leukoreduced units. No pre-medication will be permitted. Subjects will be monitored closely for any reactions during transfusion following standard hospital policy. In the event that blood units of the prespecified age are not available, patient will receive their clinically indicated transfusion with blood units of any age per hospital protocol. This would be considered a protocol deviation and those patients will then be excluded from the study

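### Aim 1 is sized at an unadjusted two-sided 0.05, but the plan also commits to adjusting comparisons within each outcome, without saying how many FMD comparisons there are, how they are adjusted, or which time point is primary

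*Combined protocol and SAP*

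**What the plan says.** All of the sizing and multiplicity text is in the combined protocol and SAP under Statistical considerations.

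- **Sizing test.** "For sample size calculations, we use the paired t-test statistic and assume a two-sided test with" alpha 0.05 and power 0.8. No multiplicity adjustment is mentioned there.
- **Sizing inputs.** The calculation cites an FMD change "of 2.4% with saRBC transfusion and a standard deviation of FMD in our lab of 3.11"%, and concludes that "with a sample size of 24 we have power to observe a 0.85% change in FMD with blood transfusion".
- **Multiplicity rule.** Later in the same section: "we will not adjust for multiple comparisons with different outcomes but will adjust for comparisons within each outcome". No method and no number of comparisons are given.

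Elsewhere in the document:

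- **Measurement times (Study Design).** "Vascular function will be assessed prior to transfusion as well as 1 hour and 24 hours after blood transfusion". This happens in both crossover periods.
- **Primary endpoint (Specific Aims, Aim 1).** "The primary endpoint of this Aim is the change in FMD with fresh vs. saRBC transfusion". No time point is attached.
- **Expectation (Expected outcomes, Aim 1).** "FMD and RHI at 24 hours post-transfusion with saRBCs will be lower than following transfusion of fresh RBCs in the same patient". The Visit #2 description adds that, in the preliminary data, the impairment was largest at 24 hours.

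**The concern.** A sample size belongs to a particular test at a particular significance level. Here the sizing uses one test at 0.05, while the multiplicity rule, read literally, applies to any outcome with more than one comparison. FMD has two post-transfusion time points per product and no designated primary one, so it is an obvious candidate for adjustment. Nothing in the text exempts the main FMD contrast. By contrast, the visit descriptions place exercise testing only on the day after each transfusion, so VO2Max has one value per period and the rule bears mainly on Aim 1.

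Two things are at stake. First, the stated power and detectable change may not describe the test that is run, and part of the alpha could go to a 1-hour comparison although the plan expects the effect at 24 hours. Second, with method, number of comparisons and primary time point all open, these choices could be made after the data are seen.

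**Working it through.** **Inputs from the plan.** n = 24; paired t-test, two-sided; alpha 0.05; power 0.80; detectable change 0.85%; SD of FMD 3.11%; FMD change in the preliminary data 2.4%.

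**Assumptions, not in the plan.** The family is the two fresh-versus-saRBC contrasts at 1 hour and 24 hours. The adjustment is Bonferroni, so each is tested at 0.05/2 = 0.025. The plan attaches 0.85% to a change with transfusion; here it is applied to the between-product contrast.

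**Step 1: the plan's own figure.** Paired t-test power comes from the noncentral t distribution with 23 degrees of freedom and noncentrality δ√24, where δ = change / SD of differences. Power of 80% at two-sided 0.05 needs δ = 0.597.

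- With 3.11% as the SD of differences, the detectable change is 0.597 × 3.11 = 1.86%, not 0.85%.
- Getting 0.85% needs an SD of differences of 0.85 / 0.597 = 1.42%, which the documents do not give.

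So 0.85% is not reproduced. That is a separate defect. In step 2 the 80% is taken as given, to isolate the effect of alpha.

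**Step 2: same effect, adjusted alpha.** Hold δ = 0.597 (noncentrality 0.597 × √24 = 2.93) and change only the critical value.

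| FMD comparisons (Bonferroni) | Alpha per test | Power for 0.85% | Change detectable with 80% power |
|---|---|---|---|
| 1 | 0.05 | 80% | 0.85% |
| 2 | 0.025 | 70.0% | 0.95% |
| 3 | 0.0167 | 63.6% | 1.00% |
| 4 | 0.0125 | 59.1% | 1.04% |
| 6 | 0.0083 | 52.6% | 1.09% |

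Normal-approximation check for two comparisons: Φ(1.960 + 0.842 − 2.241) = Φ(0.560) = 71%, in line with the exact 70%. The detectable-change multiplier is 1.116, and 0.85 × 1.116 = 0.95%. Keeping 80% power for 0.85% at alpha 0.025 would take 30 subjects instead of 24.

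**Step 3: a less strict method.** Holm with two contrasts rejects the 24-hour contrast whenever Bonferroni does, and never when an unadjusted 0.05 test would not. Its power therefore lies between 70% and 80%, depending on the 1-hour effect.

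**Step 4: how far the loss depends on effect and SD.** Power at n = 24:

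| True difference | SD of differences | Alpha 0.05 | Alpha 0.025 |
|---|---|---|---|
| 0.85% | 1.42% (implied by the stated 80%) | 80% | 70% |
| 0.85% | 3.11% | 25% | 16.5% |
| 0.85% | 3.11 × √(2 × (1 − 0.75)) = 2.20% | 44% | 33% |
| 2.4% | 3.11% | 95% | 91% |

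The third row treats 3.11% as a between-subject SD and uses the laboratory's test-retest correlation of 0.75 (FMD Reproducibility paragraph). The mismatch in alpha is present in every row; its cost in power is not constant.

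**The case against.** The strongest reply is that the plan never lists two FMD tests. A measurement schedule is not a list of hypotheses. The only Aim 1 expectation tied to a time is at 24 hours, and the Visit #2 description explains why. On that reading there is one primary contrast, alpha stays at 0.05 and no power is lost. Moreover, most analyses are planned with a mixed model. One overall product effect tested at 0.05, with adjustment only for follow-up contrasts by time, would fit the text as well. The 0.85% is also described as a change with transfusion, not explicitly as a difference between products.

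Much of this stands. Bonferroni, the family of two and the use of 0.85% for the between-product contrast are assumptions, and the 70% is conditional on them. A reader might infer that the planned FMD test has at most about 70% power. The documents do not support that as a bound. It needs Bonferroni, at least two FMD contrasts, a true difference of 0.85%, and a stated 80% that the plan's own inputs do not yield.

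What does not stand is that the plan already settles the matter. The 24-hour statements are an expectation and a rationale for a visit. They do not designate a primary time point or exempt a contrast from the adjustment rule, and the endpoint definition is silent on time. The one-contrast reading is a sensible repair, but it still has to be written down.

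**Conclusion.** The point holds as an unreconciled specification: sizing at an unadjusted 0.05, a commitment to within-outcome adjustment, and no stated method, number of FMD comparisons or primary time point. This does not depend on the SD, and a sample size recalculated at 0.05 would repeat it.

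The size is conditional. With two Bonferroni contrasts and the stated 80% for 0.85% accepted, power is about 70% and the detectable change about 0.95%; with Holm, power is between 70% and 80%. For a 2.4% difference with an SD of differences of 3.11%, the cost is about four percentage points (95% to 91%). If 24 hours is the only confirmatory FMD contrast, there is no cost, but the plan does not say so.

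The failure of 0.85% to follow from an SD of 3.11% and n = 24 should be dealt with separately. The change proposed here would not cure it.

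**What to change.** Add to Statistical considerations, and align the Aim 1 endpoint wording: the single primary Aim 1 comparison is fresh versus saRBC in change in FMD from pre-transfusion to 24 hours, tested at two-sided 0.05 without within-outcome adjustment. The 1-hour contrast and any other FMD comparisons are either tested only after the primary succeeds, in a stated fixed order, or reported as secondary with confidence intervals.

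If adjustment of the primary contrast is preferred, name the method and the number of comparisons, and restate Aim 1 power and detectable change at the adjusted alpha. With two Bonferroni comparisons and the plan's 80% taken as given, that means about 70% power for 0.85%, or 80% power for about 0.95%.

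The cost of the preferred change is a short text edit, with no added subjects or measurements. The downside is that a 1-hour FMD result could be claimed only after the 24-hour contrast succeeds.
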